13.1 Subject Disposition

The number (and %) of subjects completing the study, and discontinuing from the study, will be tabulated by treatment group, along with reasons for discontinuation. The number of subjects screened (defined as providing informed consent) and who were screen failures, along with a summary of reasons for screen failure (i.e. eligibility criteria violations), will be provided. A by-subject listing of subjects who signed informed consent but were not randomized (screen failures) including their specific reason for exclusion will also be provided. Subjects who discontinued from the study will be summarized in a by-subject listing.

The number and percentage of subjects in each treatment group in the all randomized, full analysis, and per-protocol analysis sets will be provided.

A tabulation of the number and percentage of enrolled subjects at each center will be presented.

13.2 Demographic and Baseline Characteristics

Demographic and baseline characteristics (gender, race , ethnicity, age (years) , height (cm), weight (kg), and medical history will be summarized overall and by treatment group using descriptive statistics including sample size (n), mean, std, median, Q1, Q3, minimum, and maximum for continuous variables and numbers and percentages of subjects for categorical variables. This summary will be provided for the All Randomized analysis set and the FSS, FES and PPAS.

Demographics and medical history will be provided in by-subject listings.

13.3 Treatments

13.3.1 Extent of Study Drug Exposure

For each subject, the total number of hours of drug exposure will be calculated. The total duration of exposure to investigational product (in days) will be calculated as: Date of last dose – Date of first dose + 1. Hours and duration of drug exposure will be listed.

The first dose of treatment will be defined as Day 0, as stated in the Protocol.

13.3.2 Concomitant Medications

Prior and/ or concomitant medications will be coded according to WHODRUG (Version Global B3 2017SEP01 DDE+HD (Enhanced + Herbals)).

A medication or therapy, other than the study drug, is considered concomitant with study drug if administered on or after the administration of study drug. Prior medications or therapies are those administered prior to the administration of study drug.

Prior and/ or concomitant medications will be summarized separately by treatment group and the summary will include the number and percentage of subjects who received at least one medication and the number and percentage of subjects who received at least one medication by ATC classification level 3 and preferred term. Separate descriptive summaries will be provided by treatment group for the FES and PPAS.

All medications will be provided in a by-subject listing along with a column indicating whether the medication was prior or concomitant

Handling of missing or partial dates is defined in Appendix 2.

13.4 Important Protocol Deviations

A by-subject listing of randomized subjects with any eligibility criteria violations will be provided.

The number and percentage of randomized subjects with any important protocol deviation and the number and percentage of subjects with any important protocol deviation by deviation category will be summarized overall and by treatment group. A by-subject listing of all protocol deviations will be provided with columns identifying the date of the deviation, importance (important or not important), deviation category, and the standardized and verbatim descriptions of the deviation. All important protocol deviations will be summarized by using the FES.

13.5 Efficacy Analyses

The primary efficacy endpoint for this study is the proportion of subjects who died or had respiratory failure (DRF) through Day 28.

All subjects in the ARAS will be included in the analysis of the efficacy endpoints. The DRF proportion will also be calculated for the following subgroups: race (White Caucasian vs African American vs Others), gender, age group (\leq 65 years vs $>$ 65 years), and baseline disease severity (oxygen \leq 5 vs $>$ 5 and comorbidities $<$ 2 or \geq 2).

13.5.1 Estimand

The main estimand is the odds ratio for the likelihood of DRF, comparing the INOpulse group to the placebo group.

The main estimand is defined by the following attributes:

- (1) Treatment regimens for patients to be evaluated:
INOpulse at 125 micrograms/kg IBW/hr versus INOpulse placebo
- (2) Populations of patients targeted by the clinical question:
The patients targeted in this analysis are all randomized patients, grouped according to randomized treatment assignment.
- (3) Patient-level outcome to be measured:
The outcome being measured is the likelihood of death or respiratory failure at Day 28.
- (4) Intercurrent events:
The analysis will be done regardless of the use of rescue medications, protocol violations, or investigational product discontinuation. Intercurrent events which are protocol deviations will be summarized in table format. The outcome of DRF is binary, with the event being DFR, and the non-event being any other outcome. Therefore, other modifications due to intercurrent events, such as death from another cause or a subject receiving another therapy, will not be made to the outcome variable. Death will not be considered an intercurrent event for the primary endpoint as it is part of that endpoint definition. Subjects will be analyzed using an "intent to treat" approach. Sensitivity analysis of the primary outcome using the PPAS set will be conducted to evaluate the robustness of the parameter estimate.
- (5) Population-level summary measure
The population-level summary is the estimated likelihood of DFR, adjusted for treatment, baseline oxygen level (as a continuous covariate), number of co-morbidities (as a discrete numeric covariate), and age (as a continuous covariate).

13.5.2 Type I Error Rate

A gatekeeping methodology will be utilized for the primary and secondary hypothesis testing.² This gatekeeping method controls the study-wise Type I error rate at 5% associated with the study's primary and secondary endpoint families. If the primary endpoint is found to be statistically significant, the p-value of 5% will be used to test the first of the secondary endpoints. This testing of the secondary endpoints will continue in a hierarchical manner, until one of the statistical tests is not found to be significant. If this occurs, none of the remaining secondary endpoints will be tested. The hierarchy for the secondary endpoints is shown as they are listed in Section 13.5.5. If the primary endpoint is found not to be statistically significant, then the statistical testing of the secondary endpoint family will not be performed.

2. <https://www.fda.gov/regulatory-information/search-fda-guidance-documents/multiple-endpoints-clinical-trials-guidance-industry>

13.5.3 Hypothesis Testing

Primary Endpoint (DRF): The statistical comparison of the proportion of subjects who experience respiratory failure (as defined in Section 10.0 above) or death through day 28 will be performed. Based on recent clinical experience, the overall proportion of hospitalized COVID19 patients who experience respiratory failure or death is about 15%. It is hypothesized that the INOpulse therapy will reduce the respiratory failure rate to 6%. Using a logistic regression analysis, this corresponds to an odds ratio of 0.36, meaning a 64% reduction in the likelihood of DFR for those patients in the INOpulse group. Formally, this hypotheses can be stated as follows:

$$H_0: \beta_1 = 0$$

$$H_1: \beta_1 = -1.017$$

where the estimand β_1 is the coefficient in the logistic regression model for treatment effect. A sample size of 500 patients yields a 93% statistical power to test this hypothesis, with a two-sided Type 1 error rate of

5%, for a logistic regression model with a binary covariate³. Conservatively, this estimand will be adjusted for age, baseline oxygen level, number of co-morbidities, and treatment, as described in Section 13.5.4 below.

3 F.Hsieh, D.Bloch and M.Larsen. *A Simple Method of Sample Size Calculation for Linear and Logistic Regression*. Statistics in Medicine, 17, 1623-1634. Stanford, 1998.

13.5.4 Statistical Modeling of Primary Estimand

A logistic regression model will be utilized (which will allow us to adjust for covariates) to model the outcome of the proportion of subjects who experience respiratory failure or death through day 28. The outcome variable of respiratory failure (response) will be binary (yes/no). Factors in the model will be: treatment, baseline oxygen level (as a continuous covariate), number of co-morbidities (as a discrete numeric covariate), and age (as a continuous covariate). The estimand of the effect of treatment on the likelihood of respiratory failure will be calculated as an odds ratios with a 95% confidence interval, adjusted for age, baseline oxygen level, and number of co-morbidities. A difference in proportions will also be provided as part of the overall analysis along with a 95% confidence interval (Refer Appendix 4).

Example SAS code for the logistic regression model is as follows:

```
proc logistic;
  class treatment no_comorbidities;
  model response = age baseline_oxygen_level no_comorbidities treatment;
  run;
```

Baseline NIAID score will not be adjusted for, as all patients in this trial will have ordinal scale score of 4 (hospitalized requiring oxygen) at the time of trial entry, and the baseline disease severity will already be captured to a large extent by the oxygen level requirements.

As a sensitivity analysis, the primary analysis of DRF described in Section 12 above will be repeated on the PPAS.

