7.5. Treatment Assignment

Subjects will be randomized and stratified for the use of Remdesivir for the treatment of COVID-19. In addition randomization will be stratified by: oxygen flow rate, NT-proBNP and comorbidities (diabetes, hypertension, cardiovascular disease [including ischemic heart disease, heart failure, cerebrovascular disease, peripheral vascular disease] and obesity [BMI ≥ 30]).

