17. STATISTICAL CONSIDERATIONS

This section provides a general description of the statistical methods to be used in analyzing both safety and efficacy data. The key statistical issues or considerations will be addressed. A more detailed statistical analysis plan will be provided in a separate document that will be finalized before unblinding of treatment assignment.

17.1. Primary Efficacy Analysis:

The primary analysis will be analyzed using a logistic regression model (Agresti, 2007, John Wiley and Sons) with treatment, age, gender and baseline stratification factors (used for stratified randomization) as covariates. Supportive analysis may be carried out while including other baseline subject level and site level covariates as needed (to be specified in the SAP).

The primary analysis is conducted at Day 28, however, we plan to conduct sensitivity analysis at Day 7 and Day 14 and day of discharge.

In addition, where appropriate, we plan to conduct time to event analysis to supplement the proportional analyses.

Details around the analysis plan will be provided in the SAP.

Expected Sample-Size

Initial assessment of the sample size is based on the historical experience of ~30% of hospitalized COVID-19 subjects deteriorating to needing increased respiratory support and the experience in our Emergency Expanded Access that indicates ~15% deteriorate.

Using 30% for the placebo arm and 15% for the iNO arm results in a sample size of 382 for a 1:1 randomized trial with 90% power for one-sided p-value of 0.025.

Based on this analysis, we are targeting a sample size of ~500 subjects. However, we note that the sample size may need to be re-assessed as the data on COVID-19 is rapidly evolving.

17.2. Interim Analysis:

An interim analysis for futility is planned after ~100 subjects have completed assessments through Day 28 in order to assess the failure rate in the iNO group versus placebo for the primary endpoint (death and respiratory failure). The interim analysis will be carried out by an independent external DMC based on pre specified criteria and stopping rules as detailed in the SAP.

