8.2 Randomization and Stratification

Subjects will receive placebo or iNO125 mcg/kg IBW/hr for 24 hours daily until resolution of hypoxemia, protocol defined respiratory failure, hospital discharge or Day 28, whichever occurs first. Randomization will be stratified based on the following four [2-level] factors in Table 1 below:

Table 1: Stratification Factors

Factor	Low	High
Oxygen Use	≤5 L/min	>5 L/min
NT-proBNP	<320 pg/ml	≥320 pg/ml
# of Comorbidities	0 or 1	≥2
Remdesivir use	No	Yes

The four comorbidities considered are

1. Diabetes;
2. Hypertension;
3. Cardiovascular disease (including ischemic heart disease, heart failure, cerebrovascular disease, peripheral vascular disease);
4. Obesity (BMI ≥ 30).

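### The SAP's primary logistic model drops gender, NT-proBNP and remdesivir from the protocol's covariate set without a reason, and its text and example code disagree on comorbidity coding

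*SAP*

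**What the plan says.** **Protocol.** The synopsis and section 17.1 give the primary analysis as a logistic regression "with treatment, age, gender and baseline stratification factors (used for stratified randomization) as covariates". Section 7.5 names remdesivir use as a stratification factor and continues: "In addition randomization will be stratified by: oxygen flow rate, NT-proBNP and comorbidities". Section 17.1 also says what is left open: "Supportive analysis may be carried out while including other baseline subject level and site level covariates as needed (to be specified in the SAP".

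**SAP, randomisation.** Section 8.2 keeps all four factors: "Randomization will be stratified based on the following four [2-level] factors in Table 1 below". Its Table 1 sets the levels: oxygen up to 5 or above 5 L/min, NT-proBNP below 320 or at least 320 pg/ml, 0–1 or at least 2 comorbidities, remdesivir no or yes.

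**SAP, analysis.** Section 13.5.4: "Factors in the model will be: treatment, baseline oxygen level (as a continuous covariate), number of co-morbidities (as a discrete numeric covariate), and age". Section 13.5.1(5) repeats the set: "adjusted for treatment, baseline oxygen level (as a continuous covariate), number of co-morbidities (as a discrete numeric covariate), and age (as a continuous covariate". Section 13.5.3 repeats it again: "Conservatively, this estimand will be adjusted for age, baseline oxygen level, number of co-morbidities, and treatment". The example code in 13.5.4 has the same terms but lists `no_comorbidities` in the CLASS statement. Section 13.5.5.1 (NIAID score) gives its covariates only through example code, which also puts `no_comorbidities` in CLASS.

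**The concern.** Three terms that the protocol assigns to the primary model are missing from the SAP's text and code alike, so this is not a typing slip. The only exclusion that 13.5.4 explains is baseline NIAID score. Appendix 4 lists the logistic model and its tipping-point version for the All Randomized and Per Protocol sets, and no model with the omitted terms. The subgroup list ("The DRF proportion will also be calculated for the following subgroups: race (White Caucasian vs African American vs Others), gender, age group", then oxygen and comorbidity severity) covers gender but not NT-proBNP or remdesivir. The protocol synopsis also says that changes in standard COVID-19 treatment will be handled in the stratification and in the analysis, yet the one treatment stratum is not in the model.

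Under SAP 13.5.2 the primary p-value opens the whole secondary hierarchy, so the model behind it should be unique. At present there are three candidates: the protocol's, the SAP text's and the SAP code's. Because odds ratios are non-collapsible, each also targets a slightly different conditional odds ratio, and 13.5.1 names the odds ratio as the main estimand.

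**Working it through.** **Step 1. The three models side by side.**

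| Term | Protocol 17.1 with 7.5 | SAP 13.5.4 text | SAP 13.5.4 code |
|---|---|---|---|
| Treatment, age | yes | yes | yes |
| Gender | yes | no | no |
| Oxygen | yes, scale not stated | continuous | continuous |
| Comorbidities | yes, scale not stated | numeric, 1 slope | CLASS, up to 4 slopes (counts 0–4) |
| NT-proBNP | yes | no | no |
| Remdesivir | yes | no | no |
| Slopes | 7, at one per factor | 4 | up to 7 |

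**Step 2. The plan's own figures.** SAP 8.1 and 13.5.3: N = 500, 1:1, 15% against 6%, two-sided 0.05, power 93%. Odds ratio = (0.06/0.94)/(0.15/0.85) = 0.3617 and its log is −1.017; both match the SAP. Power from the logistic information form is Φ(√(500 × 0.105 × 0.895 × 0.25) × 1.017 − 1.96) = Φ(3.486 − 1.96) = 93.6%. The unpooled two-proportion formula gives 91.3% and the pooled one 90.9%. The stated 93% is near enough to serve as the planning case.

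**Step 3. Events per slope.** Expected events = 250 × 0.15 + 250 × 0.06 = 37.5 + 15 = 52.5. Four slopes: 52.5/4 = 13.1. Seven slopes: 52.5/7 = 7.5.

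**Step 4. Size of the effect, by simulation.** There were 10,000 trials per scenario, with permuted blocks of 4 within the 16 strata and Wald tests from logistic fits.

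The documents give no covariate distributions or effects, so these are assumptions:
- Distributions: 35% above 5 L/min; NT-proBNP high in 35%; remdesivir 50%; male 55%; comorbidity count Binomial(4, 0.38); age mean 60, SD 14.
- Age: odds ratio 1.3 per 10 years.
- Oxygen and comorbidities: either linear (1.2 per L/min, 1.25 per comorbidity) or stepped at the Table 1 cut-points (2.2 and 1.5).
- Male / NT-proBNP / remdesivir: none (1/1/1), moderate (1.4/2/1.5) or strong (1.4/4/2).

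The table compares the SAP text model with the same model plus gender, NT-proBNP and remdesivir (all in %, gain in points).

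| Scenario | Power, SAP text | Power, plus 3 | Gain | Opposite calls | Null rejection, SAP text | Null rejection, plus 3 |
|---|---|---|---|---|---|---|
| Linear, none | 92.56 | 92.69 | 0.13 | 0.57 | 4.79 | 4.94 |
| Linear, moderate | 92.79 | 93.04 | 0.25 | 0.99 | 4.76 | 5.13 |
| Linear, strong | 92.81 | 93.72 | 0.91 | 1.45 | 4.22 | 5.18 |
| Step, none | 92.47 | 92.49 | 0.02 | 0.62 | 4.90 | 5.11 |
| Step, moderate | 92.20 | 92.58 | 0.38 | 1.20 | 5.05 | 5.36 |
| Step, strong | 92.92 | 93.79 | 0.87 | 1.49 | 4.14 | 4.90 |

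Opposite calls are trials in which one model gives p < 0.05 and the other does not. The null case is 15% in both arms, with a Monte Carlo SE of about 0.22 points; the highest value, 5.36, is 0.36/0.22 = 1.6 SE above 5. Repeat runs on the same assumptions with 2,000 to 2,500 trials per scenario gave 0.5–1.7% opposite calls and, in the 2,000-trial run, gains of about 0.1–1.5 points.

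**Step 5. Coding.** Numeric against CLASS comorbidities (SAP text against SAP code) changed 0.78–1.11% of calls, and 0.55–1.45% in the 2,000-trial run. With all terms in, the Table 1 strata against continuous oxygen and numeric count changed 0.81–1.23% of calls. The power difference (strata minus continuous) was −0.10 to −0.15 points if the true effects are linear and +0.07 to +0.21 if they are stepped.

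**Step 6. A second set of assumptions.** With 3,000 trials, the seven-slope strata model rejected under the null in 5.0% and 5.8% of trials, and the SAP text model in 4.8% and 5.2%. The SE is √(0.05 × 0.95/3000) = 0.4 points. Median treatment log odds ratios differed between the models by up to about 0.04.

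**The case against.** **The SAP governs.** Protocol section 17 calls itself a general description and refers details to the SAP. The SAP is final, states the reduced set in three places, and says the final analyses are those it outlines. It stands that a programmer would probably follow the SAP on the covariate list. It does not stand as a justification: the protocol names the primary covariates and leaves to the SAP additional ones for supportive analyses. That does not extend to removing named terms without comment.

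**Parsimony.** With about 52.5 events, a four-slope model is a respectable choice, and a reduced set that was reasoned and stated in both documents would also end the conflict. No reason is stated, however, and the SAP's own CLASS code can already use seven slopes.

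**Small and assumption-driven.** This stands. Even when the three terms have no effect, adding them changes 0.57–0.62% of calls. Real prognostic effects add only about 0.4–0.9 points to that.

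**The code is only an example.** For the primary model this largely stands, because the prose says numeric and 13.5.1(5) agrees. It does not help 13.5.5.1, where the code is the only statement of the covariates.

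**A stronger reading.** A reader might infer that continuous oxygen and a numeric count contradict the protocol. The documents do not settle that. The protocol gives no cut-points and no scale; the two-level form appears only in SAP Table 1. The protocol's reference to factors used for stratified randomisation identifies them, and entering them as strata is one reading of it. The SAP's versions carry the same two factors on a finer scale.

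**Conclusion.** The omission of gender, NT-proBNP and remdesivir is an unexplained departure from the protocol's primary model, and nothing in either document cures it. The numeric-versus-CLASS disagreement is a smaller, separate defect. Both should be fixed before unblinding because the repair costs almost nothing.

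The practical effect is small: about 0.5–1.7% of significance calls and about 0 to 1.5 points of power for the three terms. Those sizes rest on the assumed covariate distributions and odds ratios. The textual conflict does not.

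A reader might also infer that leaving out stratification factors makes the primary test invalid. The calculations do not support that. The SAP text model rejected in 4.1–5.1% of null trials in the main runs, and was slightly conservative when the omitted factors were strongly prognostic.

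**What to change.** Before treatment assignments are released:

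1. Amend SAP 13.5.1(5), 13.5.3, 13.5.4 and the example code to add gender, NT-proBNP stratum (<320 / ≥320 pg/ml) and remdesivir (no/yes).
2. State one form for oxygen and comorbidities. Continuous oxygen with a numeric count is acceptable: take `no_comorbidities` out of CLASS and note the choice. CLASS then holds treatment, gender, NT-proBNP stratum and remdesivir. MODEL holds age, gender, oxygen level, comorbidity count, NT-proBNP stratum, remdesivir and treatment. The Table 1 strata (≤5 / >5 L/min; 0–1 / ≥2) are equally acceptable. Neither form is clearly better on power, but one must be chosen, since the choice itself moves about 1% of calls.
3. State the comorbidity coding in words in 13.5.5.1.

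**Cost.** One SAP amendment by the route in SAP 6.0. No protocol change is needed, because the protocol's covariate set is restored and it fixes no scale. No new data are needed: the strata are known at randomisation and sex is recorded at screening. The statistical price is about 7.5 expected events per slope instead of 13.1.

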13.5.5 Secondary Endpoints

Secondary efficacy analyses will be performed on the secondary endpoints using the subjects in the ARAS.

Summary measures of the secondary endpoints (i.e. totals, means, proportions) will also be calculated for the following subgroups: race, gender, age group (≤ 65 years vs > 65 years), and baseline disease severity (oxygen ≤ 5 vs > 5 and comorbidities < 2 or ≥ 2).

13.5.5.1 NIAID Score

Clinical status using an 8-point NIAID ordinal scale (Table 2 above) will be assessed on days 7, 14, 28 and Day of Discharge. Descriptive statistics (totals and percentages) will be summarized for subjects overall, and by treatment group and day of assessment. The effect of treatment on NIAID score over time will be evaluated using a mixed effects model with repeated measures (MMRM). The estimand will be the slope of the regression coefficient for the treatment effect, adjusted for covariates as shown in the example SAS code below:

```
proc mixed method=ml covtest;
  class patient treatment no_comorbidities;
  model NIAID_Score = age baseline_oxygen_level no_comorbidities treatment / s;
  repeated / type=un subject=patient r;
  run;
```

The significance of model coefficients will be evaluated using F tests.

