13.0 Statistical Methods

All analyses will use SAS version 9.4 or higher.

Data from all study sites will be pooled for analyses.

Unless otherwise noted, all summaries will be provided by treatment group: INOpulse and placebo. Demographic summaries will also be provided by stratification group (separately for each stratification factor, described in Section 8.2 above) as a subgroup analysis.

Unless otherwise noted, continuous variables will be summarized using number of observations (n), mean, standard deviation (std), median, first quartile (Q1), third quartile (Q3), minimum and maximum values. The minimum and maximum values will be displayed to the same level of precision as the raw data; the mean, median, Q1 and Q3 values to one additional decimal place and the std to two additional decimal places.

Categorical variables will be summarized using counts and percentages. Percentages will be rounded to one decimal place, except 100% will be displayed without any decimal places and percentages will not be displayed for zero counts.

All participants will be used in the analyses, as per the analysis populations described in Section 11.0 above, using all non-missing data available. Missing data in the logistic regression analysis of DFR will be analyzed as follows: If there is missing data for more than 5% of the cases for the outcome variable, a tipping point analysis will be performed. This will be done as a sensitivity analysis to determine whether or not the data is missing at random, and if the data is not missing at random, how robust is the parameter estimate in the model. The MI and MIANALYZE procedures in SAS¹ will be used to perform this analysis.

As a secondary sensitivity analysis, if there is missing data for more than 5% of the subjects at any time point in the NIAID assessments, the MI procedure in SAS will be utilized to impute missing values for NIAID score, and the statistical models will be run again using the imputed data points to compare the validity of the results using MIANALYZE.

1. SAS/STAT 14.2 User Guide. 2016, 6130 – 6135. SAS Institute Inc., Cary, NC.

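### The NIAID repeated-measures model that gates the later secondaries has no visit term: it tests one pooled coefficient with unstated visit weights and gives no effect over time

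*SAP*

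**What the plan says.** SAP 13.5.5.1 states the aim: "The effect of treatment on NIAID score over time will be evaluated using a mixed effects model with repeated measures (MMRM"). It then defines the target: "The estimand will be the slope of the regression coefficient for the treatment effect", adjusted as in the example SAS code that follows. In that code the CLASS statement holds patient, treatment and number of comorbidities; the model is "model NIAID_Score = age baseline_oxygen_level no_comorbidities treatment / s"; and the covariance statement is "repeated / type=un subject=patient r". Visit appears in none of the three. The scale "will be assessed on days 7, 14, 28 and Day of Discharge". Results by day are otherwise descriptive (totals and percentages), and Appendix 4 lists by-time-point summaries and a single mixed-model table, 14.2.2.2.

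SAP 13.5.2 tests the secondaries in sequence after a significant primary: "The hierarchy for the secondary endpoints is shown as they are listed in Section 13.5.5", where NIAID comes first. On a non-significant step: "If this occurs, none of the remaining secondary endpoints will be tested".

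SAP 13.0 adds a rerun: "As a secondary sensitivity analysis, if there is missing data for more than 5% of the subjects at any time point" of the NIAID assessments, the same models are refitted to multiply imputed scores. Table 4 of that section gives Days 7, 14 and 28 windows of ±3 days, takes the latest record in a window, and leaves discharge outside these windows.

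**The concern.** A model without visit fits one mean level for all days and one treatment coefficient. It cannot show whether an effect appears early, persists, fades or reverses, although the stated aim is the effect over time. Three things follow.

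- The coefficient is a weighted average of the visit effects, and the plan neither states nor controls the weights.
- If mean scores change over time and one arm misses more of a given visit, part of the time trend is read as a treatment effect.
- With no repeated effect named, the software pairs records by their order within patient. If missed rows are dropped rather than kept as blanks, a Day 14 score can be treated as a Day 7 score.

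The test decides whether recovery, discharge, hospital duration, mortality and RT-PCR conversion are tested at all. A day-of-discharge record has no fixed day and exists only for discharged subjects, so including it would also let the number of records differ by arm.

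**Working it through.** The plan gives no NIAID effect size, SD, power or missing rate, so it has no figure to reproduce. From the documents: 500 subjects, 1:1, two-sided 5% (SAP 8.1). Means, SDs, correlations and missing rates below are assumptions. Age, oxygen and comorbidity covariates are left out.

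**1. Visit weights, complete data.** Let V be the within-arm covariance matrix of the Day 7, 14 and 28 scores. The maximum-likelihood pooled coefficient tends to w′e, where e holds the three visit effects and w = V⁻¹1 / (1′V⁻¹1). For given V the mean course does not alter w, but on a bounded 1–8 scale V itself moves with the means.

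Example with equal SDs and correlations 0.6 (Days 7–14), 0.45 (7–28) and 0.6 (14–28). By symmetry the unscaled weights are a, b, a, with 1.45a + 0.6b = 1 and 1.2a + b = 1. So 0.73a = 0.4, a = 0.548, b = 0.342, sum 1.438, and w = 0.38/0.24/0.38.

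| Setting | SDs, Days 7/14/28 | Correlations (7–14, 7–28, 14–28) | Weights, Days 7/14/28 |
|---|---|---|---|
| Flat | 1.8/1.8/1.8 | 0.6, 0.45, 0.6 | 0.38/0.24/0.38 |
| Steep | 1.4/1.5/1.3 | 0.6, 0.45, 0.6 | 0.39/0.09/0.52 |
| Rising SD | 1.2/1.5/1.7 | 0.6, 0.5, 0.75 | 0.75/0.15/0.10 |
| Rising SD, higher correlation | 1.2/1.6/2.0 | 0.75, 0.65, 0.8 | 1.01/0.08/-0.08 |

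A late effect of 0.1/0.35/0.6 (simple mean 0.35) becomes:
- flat: 0.038 + 0.084 + 0.228 = 0.35
- steep: 0.039 + 0.032 + 0.312 = 0.38
- rising SD: 0.075 + 0.053 + 0.060 = 0.19

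Effects of +0.4/0/-0.4 average zero. Under the rising-SD weights they give 0.75×0.4 - 0.10×0.4 = 0.26, significant in about 69% of simulated trials. Under the flat weights they give 0.

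**2. Validity under the null.** In 2000 simulated trials per setting (250 per arm), the SAP model rejected in 4.7–5.5% with complete data and in 4.9–5.1% with 10% of Day 28 scores missing in both arms. With complete data, adding a visit main effect left the estimate and rejection rate unchanged (5.2% either way).

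**3. Unequal missingness, true effect zero, random within arm, 20% iNO v 5% placebo.**
- Day 7: bias +0.01 to +0.06 points across the settings. Simulated rejection was 5.5–6.8% for +0.01 to +0.04.
- Day 28: large-sample bias -0.017 (flat, means 6.0/6.1/6.4), -0.038 (steep, means 5.0/6.2/7.0), -0.006 to -0.009 (rising SD, means 5.0/6.3/7.0, correlations 0.5–0.75), and +0.004 (last row of the table, means 5.5/6.2/6.6). Simulated rejection was 5.2–7.0%.

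The two days differ because Day 28 carries 0.38–0.52 of the weight in the first two rows and 0.10 or less in the last two.

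**4. Is such an imbalance likely?** Suppose both arms miss 20% of post-discharge calls and iNO lowers deterioration from 15% to 6%. Even if each averted deterioration became a discharge, the imbalance would be at most 0.20 × 9 = 1.8 points; in simulation it was about 1 point per visit. Gaps of 15 points or more are stress cases.

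**5. Rows paired by order.** With missed Day 7 rows dropped, 5% iNO v 15% placebo, bias moved from about -0.05 to -0.10 and rejection from about 6% to 13%. At 5% v 25% it moved from -0.09 to -0.21 and from 11% to 47% (250 trials each, so approximate). With 15% of Day 7 rows absent in both arms, rejection was 5.7–5.8%.

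**6. With visit and treatment-by-visit terms.** The equal-weight Day 7/14/28 average had bias of at most 0.005 and rejection of 4.7–5.7% in all Day 28 settings. Effects of +0.4/0/-0.4 were recovered as +0.39/0.00/-0.40.

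**The case against.** The strongest reply is that the test is valid as it stands and the wording merely loose. Much of this holds. Rejection stays near 5% with complete or equally missing data. The bias needs unequal missingness that the documents do not predict. Daily inpatient scoring, telephone contacts after discharge and the ±3-day windows in SAP 13.0 all limit missing scores.

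A reader might infer that the effect tested at the gate contradicts the one defined. The documents do not support that: the estimand sentence points to the code, so its plain reading is the treatment coefficient in that code, loosely called a slope. A reader might also infer that an arm missing more late scores always looks worse. That fails too, since the Day 28 bias ranges from slightly negative to slightly positive with the covariance.

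Other replies do not remove the point. The code is labelled an example, but the estimand refers to it and no other model is given. The imputation rerun is a sensitivity analysis of the same models, so it neither decides the gate nor supplies an effect over time. The windows do not say whether day-of-discharge rows enter the repeated measures.

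**Conclusion.** The specification gap stands and should be fixed. The model named for evaluating the effect over time cannot show one, and it fills the first gated step with a pooled coefficient whose visit weights the plan leaves to chance. This holds even with no missing data and is the main cost.

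The bias is secondary: small, dependent on assumptions and absent when missingness is equal. At 20% v 5% it is about +0.01 to +0.06 points for the arm missing more Day 7 scores, and about -0.04 to 0 at Day 28 with no fixed sign. It can be larger if missed rows are dropped and records are paired by order. All sizes rest on assumed means, SDs, correlations and missing patterns. They do not show that type I error at the gate is materially inflated in practice. The primary analysis is unaffected, and the gate matters only if the primary succeeds.

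**What to change.** Amend SAP 13.5.5.1 before unblinding:

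- Add visit to CLASS, with levels Day 7, 14 and 28 only.
- Use `model NIAID_Score = age baseline_oxygen_level no_comorbidities treatment visit treatment*visit / s;`
- Use `repeated visit / type=un subject=patient r;`
- Replace the slope wording with one named gate contrast, for example the treatment difference averaged with equal weight over Days 7, 14 and 28. The choice is the sponsor's.
- Output it explicitly, for example `lsmeans treatment / diff cl;` for the average and `lsmeans treatment*visit / diff cl;` for the three visit differences, which are reported without further gating. Without such a statement, the treatment coefficient printed by `/ s` is, under default coding, the effect at the last visit.
- State that day-of-discharge records stay out of the repeated measures and in the descriptive table.

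The cost is SAP text and code, with no new data. Power may rise or fall. In one assumed course with median discharge about 6 days, the present model against the equal-weight average gave 71 v 67% for a constant effect, 50 v 67% for an early one and 88 v 67% for a late one; in the flat course both gave 74%. Visit terms do not remove all bias if missed calls depend on discharge status: with Day 28 calls missed by 20% v 5% of discharged subjects, bias fell from -0.057 to -0.014, not to zero.
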